1.7 Population to be Studied

This study will enrol male and female subjects with a painful abdominal or thoracic scar. Pain should be rated as moderate to severe i.e. numerical rating scale (NRS) score between 4 and 8 on an 11-point scale (0-10), and stable within one month before screening. The pain should also be chronic, i.e. persistent for more than six months after the surgery which led to the painful scar.

To ensure subjects will potentially benefit from intradermal injection of Dysport, they will be tested for responsiveness to local anaesthetic (lidocaine) during a pre-randomisation run-in period. This is consistent with use of diagnostic local anaesthetic blocks which are used to obtain information about of the source of subject's pain, being target specific and controlled in order to exclude false positive results (Bogduk, 2002). This assessment will be performed by investigators with experience in managing subjects with painful conditions and pain studies.

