3 INVESTIGATIONAL PLAN

3.1 Overall Study Design and Plan

The study will consist of two sequential parts, the first being to identify subjects who will potentially benefit from intradermal Dysport injection, 'responders', who will then progress to the second part, which is the double-blind study of the intradermal injection of Dysport or placebo:

- Part A: A double-blind, randomised, initial two-period cross-over run-in part, extended screening period of placebo or local anaesthetic (lidocaine),
- Part B: A single-dose, double-blind, randomised, parallel part with one of the three different doses of Dysport or placebo.

To ensure subjects will potentially benefit from intradermal injection of Dysport, they will be tested for responsiveness to local anaesthetic (lidocaine).

In Part A, and upon consent and successful screening of medical eligibility, subjects will be injected (injection test 1) during a pre-randomisation run-in period in a double blind fashion with either saline or local anaesthetic (lidocaine) and assessed for pain perception up to 24 hours post-injection. One week later, they will be crossed over, injected with the other agent (injection test 2) and assessed for pain perception up to 24 hours post-injection. Pain intensity will be scored using a 11-point NRS (from score 0 for "no pain" up to 10 for "worst possible pain").

If subjects are assessed as responders, they will enter in Part B, and will be trained and provided with an Actiwatch® to enable them to record twice a day their spontaneous NRS scores.

[figure not shown]
Before dosing on Day 1, the subjects will perform baseline assessments including a quantitative sensory testing (QST) assessing allodynia, hyperalgesia and conditioned pain modulation, completion of a QoL questionnaire, and safety assessments (physical examination, vital signs measurements, collection of adverse events (AEs) and recording of concomitant medication).

Subjects will be dosed if considered as consistent in pain perception from the screening visit (i.e. variability < 2 for the average spontaneous NRS score pre-injection tests in Part A, pre-QST and pre-dosing and as clinically plausible per investigator's judgement).

Subjects will then be assessed for pharmacodynamics and safety for a total of 16 weeks post-dose.

Subjects will be discharged from the study after safety assessments (physical examination, vital signs) during an end of study (EoS) visit.

The study design is presented in [Figure 2](#).

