Two types of code-break envelopes will be set up for the pre-randomisation run-in period (Part A) and for the randomised double-blind period (Part B).

Two sets of individual sealed code-break envelopes of each type will be prepared by the sponsor's randomisation manager to enable emergency code-break procedures for individual subjects without compromising the blind of the study. One set will be provided to the CRU and one set provided to the sponsor department of global patient safety (GPS).

In an emergency situation, which requires the identification of the study treatment group, the investigator may break the treatment code. If so, the investigator is requested to:

- Inform the monitoring office at the earliest opportunity that the blind has been broken for an emergency situation,
- Reseal the code-break envelope,
- Sign, date and provide reason for the code-break on the emergency code-break form, and on the sealed envelope.

The date and reason for code-breaking should also be recorded in the electronic case report form (eCRF).

Specific case, to check if the subject is a responder at the end of the run-in period, the investigator will unblind the subject by (re)-opening the code-break-envelope associated to his/her assigned pre-randomisation run-in number. The investigator will sign, date and specify "End of run-in period" as the reason for the code-break on the envelope.

Monitors should routinely check the integrity of the envelopes that are stored at the study site. They must collect envelopes from the study site prior to study close-out and ensure that they are all intact. If envelope(s) have been opened at the site or by the sponsor's representative, the monitor must ensure a written explanation is clearly documented (opener's name, dated signature and reason for opening) on the visit status page of the eCRF.

Confirmation of the integrity of all code-break envelopes at study completion must be documented in the trial master file (TMF). All sets of the sealed individual subject envelopes must be kept in the TMF in the co-ordinating office at study completion for proof of integrity.

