5.2.2 Pre-randomisation Run-in Period (Part A)

After successful screening of medical eligibility and within 21 days maximum before IMP dosing on Day 1, subjects will come back to the CRU for an injection test 1 visit, they will receive a pre-randomisation run-in number and be injected in a double blind fashion with either local anaesthetic (lidocaine) or placebo (saline).

They will be assessed for pain perception on site and then be discharged from the CRU from 1 hour post-injection test 1 and continue to record their NRS score at home as described in Section 9.1.2. They will be contacted by telephone by the site to check their safety and collect

their NRS score post-injection test 1 at the end of the injection test 1 day and on the following day.

Approximately one week later and within 14 days maximum before IMP dosing on Day 1, they will come back to the CRU for injection test 2. They will be crossed over and injected with the other agent.

They will be assessed for pain perception on site and then be discharged from the CRU from 1 hour post-injection test 2 and continue to record their NRS score at home as described in Section 9.1.2. They will be contacted by telephone by the site to check their safety and collect their NRS score post-injection test 2 at the end of the injection test 2 day and on the following day. After completion of subject's injection test 2, the blind will be broken by an investigator to check if the subject is a responder.

Subjects will be considered as responders and randomised to Part B if:

- The pattern of pain relief is sufficiently greater with lidocaine than saline using the formula below:

$$[\text{NRS}_{\text{predose}} - \text{NRS}_{\text{1 hour post-injection test}}]_{\text{placebo}} - [\text{NRS}_{\text{predose}} - \text{NRS}_{\text{1 hour post-injection test}}]_{\text{lidocaine}} \geq 2$$
- The pattern of pain relief is clinically plausible in the investigator's opinion, e.g. onset of pain relief reported by 30 min from time of completing the injections, pain scores after the lidocaine injection test rising again by 2-8 hours post-injection,
- The investigator has no concern regarding compliance with study procedures and safety.

Albeit considered unlikely, should the results be equivocal, or if an unexpected but plausible pattern of response emerges, the decision as to whether a subject should proceed in the study, will be adjudicated by mutual agreement of the investigator and the sponsor.

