18 ATTACHMENTS

18.1 Attachment 1 – Study Schedule of Assessments

Study Procedures	Screening D-28 max	Injection test 1 D-21 max	Injection test 2 D-14 max	Baseline from D-7 max	D1 pre- dose	D1 post- dose	D2-D7	W2 [a]	W4 [a]	W6 [a]	W8 [a]	W10 [a]	W12 [a]	W14 [a]	W16 EoS/ ED [a]
Part	Screening	Part A		Part B											
Informed consent	X														
Clinic visit	X	X	X	X	X					X			X		X
Subject call		X [b]	X [b]	X [c]			X [d]	X [d]	X [d]		X [d]	X [d]		X [d]	
Eligibility check	X			X	X										
Demography	X														
Medical and surgical history	X														
Drug of abuse	X														
Urine pregnancy test (female subjects only)	X				X										X
Physical examination	X			X	X					X [f] [g]					X
Vital signs	X [e]	X [g]	X [g]	X [g]	X [g]	X [g]				X [g]					X [g]
ECG, Safety lab	X														
Scar ultrasound	X														
Painful area mapping	X	X	X	X	X [h]					X			X		X

Study Procedures	Screening D-28 max	Injection test 1 D-21 max	Injection test 2 D-14 max	Baseline from D-7 max	D1 pre-dose	D1 post-dose	D2-D7	W2 [a]	W4 [a]	W6 [a]	W8 [a]	W10 [a]	W12 [a]	W14 [a]	W16 EoS/ ED [a]
Pre-randomisation Part A		X													
Lidocaine/placebo injection (saline)		X	X												
NRS score collection and diary providing		X [i]	X [i]												
Actiwatch® training and providing				X											
Randomisation in Part B					X										
Dysport/placebo injections						X									
Spontaneous NRS	X [j]	X [k]	X [k]	X [l]	X [l]	X [l]	X [l]	X [l]	X [l]	X [l]	X lk]	X [l]	X [l]	X [l]	X [l]
Rescue medication diary provided						X									
Reminder about analgesia washout 12-hour period pre-injections or QST		X	X	X	X			X	X	X	X	X	X	X	
QST (stimulus-evoked NRS)				X [m]						X [m]			X [m]		
QoL (SF-36)				X						X			X		
Concomitant medications and adverse events	X	X	X	X	X	X	X	X	X	X	X	X	X	X	X

a Visit to be performed \pm 3 days around the scheduled date.

b In the evening and on the following morning to check safety and collect spontaneous NRS scores.

- c Once the NRS scores from injection tests 1 and 2 are known and blind has been broken, the subject's responder status is determined. Subjects will be contacted by telephone by an investigator to inform of the result, and in the case of responders, they will enter in Part B.
- d Subjects will be contacted by telephone by the CRU every day up to Day 7 and every 2 weeks after IMP dosing for collection of AEs, concomitant medications and compliance with pain assessments and other study requirements.

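### The Part A responder formula is printed with its two terms reversed: it is met only when saline relieves pain by at least 2 NRS points more than lidocaine

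*Protocol*

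**What the plan says.** Part A is a crossover run-in with lidocaine and saline, used to choose who goes on to Part B. Protocol Section 1.7 gives its purpose: "To ensure subjects will potentially benefit from intradermal injection of Dysport, they will be tested for responsiveness to local anaesthetic (lidocaine").

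Section 5.2.2 sets three conditions for being a responder and being randomised to Part B:

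1. A numerical comparison of the two agents, introduced by "The pattern of pain relief is sufficiently greater with lidocaine than saline using the formula below". The formula that follows is: [NRS predose − NRS 1 hour] on placebo, minus [NRS predose − NRS 1 hour] on lidocaine, ≥ 2.
2. A pattern of relief that the investigator finds clinically plausible. The examples given are onset by 30 minutes, and scores rising again 2 to 8 hours after lidocaine.
3. "The investigator has no concern regarding compliance with study procedures and safety".

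Equivocal results, or unexpected but plausible ones, "will be adjudicated by mutual agreement of the investigator and the sponsor".

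The decision is made at the site after the Part A blind is broken. Section 3.4.3 says that "to check if the subject is a responder at the end of the run-in period, the investigator will unblind the subject", and footnote c of the schedule in Attachment 1 places the determination at the same point: "Once the NRS scores from injection tests 1 and 2 are known and blind has been broken".

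The Amendment 2 summary (Attachment 6) reproduces the formula in the same order. The SAP does not restate it.

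**The concern.** The sentence and the formula point in opposite directions. The sentence wants lidocaine to give clearly more relief than saline. The formula, read as printed, wants saline to give clearly more relief than lidocaine.

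This is the only numerical threshold in the protocol that compares the two agents, and it controls entry to Part B. Applied literally, it would turn away the lidocaine responders the trial is looking for and let through, on this condition, subjects who did better on saline. With about 24 subjects planned, six per arm, a few misclassified subjects would change the population being described.

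The other numerical entry conditions would not reveal a reversal. Before dosing, Section 3.1 requires "variability < 2 for the average spontaneous NRS score pre-injection tests in Part A, pre-QST and pre-dosing". That concerns the stability of pain scores and treats the two agents alike. The screening limits (NRS 4 to 8, pain axis of at most 10 cm) do not concern lidocaine response at all.

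**Working it through.** **Inputs**

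- NRS direction: 0 is no pain, 10 is worst possible pain (Protocol Section 3.1).
- Predose score: current pain just before the injection test (Section 9.1.2).
- Placebo in Part A: saline (Section 3.4.1.1).
- Threshold: 2 points (Section 5.2.2).

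**Sign of each term.** Let P = predose − 1 hour on saline and L = predose − 1 hour on lidocaine. Since lower scores mean less pain, P and L are relief, positive when pain falls.

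- Printed rule: P − L ≥ 2.
- Rule the sentence describes, with the same threshold: L − P ≥ 2.

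The two cannot hold together: the first needs P > L, the second L > P.

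**Worked cases**

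| Saline | Lidocaine | P | L | Printed P − L | Printed rule | Exchanged L − P | Exchanged rule |
|---|---|---|---|---|---|---|---|
| 6 to 5 | 6 to 2 | 1 | 4 | −3 | not met | +3 | met |
| 6 to 2 | 6 to 5 | 4 | 1 | +3 | met | −3 | not met |
| 6 to 6 | 6 to 2 | 0 | 4 | −4 | not met | +4 | met |
| 6 to 5 | 6 to 3 | 1 | 3 | −2 | not met | +2 | met |
| 6 to 4 | 6 to 4 | 2 | 2 | 0 | not met | 0 | not met |

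**All integer score patterns.** Every combination of predose and 1-hour scores on the two agents was enumerated, with 1-hour scores from 0 to 10. The predose range of 4 to 8 is an assumption: inclusion criterion 4 applies to spontaneous pain at screening, not to current pain on the test day. The range 0 to 10 is shown alongside. Predose scores differing by less than 2 serve as a proxy for the variability condition.

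| Set | Total | Printed only | Exchanged only | Both | Neither |
|---|---|---|---|---|---|
| Predose 4–8 | 3,025 | 1,165 | 1,165 | 0 | 695 |
| Predose 4–8, predose difference < 2 | 1,573 | 589 | 589 | 0 | 395 |
| Predose 4–8, no worsening on either agent | 1,225 | 395 | 395 | 0 | 435 |
| Predose 0–10 | 14,641 | 5,995 | 5,995 | 0 | 2,651 |
| Predose 0–10, predose difference < 2 | 3,751 | 1,405 | 1,405 | 0 | 941 |

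In the first set the classification reverses in 1,165 + 1,165 = 2,330 of 3,025 patterns (77.0%). Without worsening it reverses in 790 of 1,225 (64.5%). In no set does a pattern with L ≥ P meet the printed rule. These count possible patterns, all weighted equally; they do not predict how many subjects are affected.

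**Alternative reading.** If each bracket were written as 1 hour minus predose with the agents left in place, the rule becomes (−P) − (−L) = L − P ≥ 2, which is the exchanged rule. So the error is a single sign, and either correction gives the same criterion.

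**The case against.** The best reply is that this is an obvious slip which no competent site would follow. The introducing sentence, the lidocaine example in the second condition and the stated purpose of Part A all point one way. Entry also requires a plausible pattern and no investigator concern, so passing a reversed formula is not enough. Of the 1,165 patterns that meet only the printed rule (predose 4–8), just 270 show any lidocaine relief at 1 hour. The other 895 would struggle to match the example of relief that then wears off. Literal use would more probably exclude true responders, and produce a visible shortage of entrants, than quietly enrol saline responders. Finally, the criterion acts before Part B randomisation, so it does not bias the comparison between arms.

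Much of this stands. It limits the likely harm, and it means the consequence concerns which population is studied rather than the validity of the randomised contrast. The percentages also depend on the grid chosen, as the fall from 77.0% to 64.5% shows, and the argument does not need them.

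It does not remove the contradiction. The 30-minute and 2-to-8-hour figures are examples under investigator judgement, not thresholds. Adjudication covers equivocal or unexpected results, and wrongly excluding a clear lidocaine responder need not trigger it. The SAP plans a table of non-responders (Section 5.2), deviation listings (Section 5.3) and a listing of Part A NRS scores (Section 5.7.2). A reader could work out the difference from that last listing, but no planned output recomputes the criterion.

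**Conclusion.** The concern holds. As printed, the formula is met only when saline relief exceeds lidocaine relief by at least 2 points, which contradicts the sentence it is meant to implement. The result rests only on the direction of the NRS and the order of the terms; it needs no assumption about score ranges. For any subject whose relief differs by 2 points or more between agents, the printed formula gives the wrong answer to the question the sentence asks. For smaller differences nothing changes.

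The documents do not show which direction was applied, so misapplication is neither established nor excluded. Because this threshold controls entry to Part B, it must be corrected.

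**What to change.** In Protocol Section 5.2.2, exchange the two bracketed terms and leave the threshold as it is: [NRS predose − NRS 1 hour] on lidocaine, minus [NRS predose − NRS 1 hour] on placebo, ≥ 2. This adds no new rule; it makes the formula agree with its own sentence. Confirm and document which direction was used for every subject already assessed.

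In the SAP, keep responder status as recorded under the three conditions and the adjudication route. As a worthwhile but separable addition, derive the lidocaine-minus-placebo relief difference and show it beside the recorded status in the Part A listing of Section 5.7.2. Flag any Part B subject who does not meet the corrected criterion, noting whether entry was by adjudication.

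The cost is one protocol line, one derived variable and one flag in a listing already planned. No new data are needed: Protocol Section 12.3 has NRS data collected for run-in failures too.

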5.2.3 Randomised Double-blind Period (Part B)

5.2.3.1 Baseline visit

A QST (including light touch, pressure, temperature as stimuli) [stimulus-evoked NRS] and completion of QoL questionnaire SF-36 will be performed within 7 days prior to Day 1. Subjects will also receive a training on how to use their Actiwatch® (device to be used for collection of the spontaneous NRS score). They will start to enter their NRS scores in their Actiwatch®, and will be provided with a paper diary as a back-up solution for NRS score collection.

5.2.3.2 Randomised Period

The subjects will be required to attend the CRU on several occasions during the study:

- On Day 1 in the morning, based on investigator judgement, some of the screening/run-in assessments may be redone to confirm that subjects are still compliant with the inclusion/exclusion criteria and study restrictions. If the subject is considered as stable in pain perception from the screening visit, subjects will undergo pre-dose safety

assessments and then receive the dose of IMP. After IMP dosing, subjects will undergo post-dose assessments as described in Section 18.1.

They will be instructed to continue entering their NRS score in the Actiwatch® and will be provided with a paper rescue medication diary to note their post-dose rescue medication intake (i.e. for scar pain) and NRS score immediately before intake at home (details on rescue medication are provided in Section 6.2).

They will be discharged after a minimum of two hours post-dosing.

- Out-patient visits: Subjects will be required to come back to the CRU for out-patient visits on Week 6 and Week 12.

During the randomised double-blind period (Part B), subjects will also be contacted by telephone by the CRU every day up to Day 7 (subjects might visit the CRU if required for safety purpose) and every two weeks after IMP dosing for collection of AEs, concomitant medications and compliance with pain assessments and other study requirements.

The outpatient visits and calls from Week 2 post-dosing can occur +/- three days around the scheduled date.

5.2.4 Early Discontinuation or End of Study Visit

Subjects will be discharged from the study after completion of an EoS visit for follow-up assessments which will happen 16 weeks after the IMP dosing +/- three days or earlier in case of early discontinuation (ED). The principal investigator will inform the family doctor and pain clinic (if applicable) with details of participation in the clinical study and any relevant information which may help the treating physician in the management of their patient.

5.3 Lifestyle Restrictions

5.3.1 Diet

As poppy seeds can cause a positive result on the drug of abuse (DOA) test, subjects will be advised to avoid eating poppy seeds/food containing poppy seeds for at least 24 hours before attending any DOA test. Subjects diet is expected to remain stable for the duration of the study.

5.3.2 Alcohol

Subjects should abstain from alcohol for 24 hours prior to each visit to the CRU. Excessive alcohol consumption (>21 units per week) should be avoided for the duration of the study.

5.3.3 Physical Activity

Subjects should not change their exercise regime from screening until completion of the study.

5.3.4 Prohibited Concomitant Medications and non Drugs Therapies

The following medications and therapies should not be started during the study:

- Physiotherapy,
- Transcutaneous electrical nerve stimulation therapy,
- Antidepressants and anxiolytics,
- Anticonvulsant medication used to treat pain,
- Opioids

- Non steroidal anti-inflammatory drugs except for brief periods of treatment (up to two days) for other pain or fever,
- Acetylsalicylic acid (aspirin) except for low doses taken for cardioprotection or brief periods of treatment (up to two days) e.g. for episodes of fever,
- Corticosteroids (injected to treat the scar pain),
- Local anaesthetics (injected to treat the scar pain, unless for the pre-randomisation run-in period),
- Medications listed in the exclusion criteria.

Rescue medication (as detailed in Section 6.2, i.e. paracetamol up to 4000 mg per day in divided doses which can be substituted by co-codamol 30 mg/500 mg for the first week post-IMP administration) is allowed except within 12 hours before QST assessments. Subjects must not take medication containing paracetamol and rescue medication without having discussed this with the investigator.

Subject will also be cautioned on the use of any other medication (over-the-counter or prescription containing paracetamol e.g. Lemsip®).

5.4 Priority Order on Study Procedures

The following priority order should be followed in case study procedures are scheduled at the same timepoint:

- (1) NRS,
- (2) Vital signs,
- (3) Physical examination,
- (4) ECG,
- (5) Blood sampling,
- (6) QST,
- (7) Actiwatch® training.

